12.2 Determination of Sample Size

For TTSTAND (calculated as a velocity, defined as rise per second), the sample size of 74 participants has been calculated using the following values:

- Mean difference = 0.05
- Standard deviation = 0.075
- Type I error level (two-sided) = 0.05
- Power level = 0.8
- Allocation ratio (N1: viltolarsen/N2: placebo) = 1

The mean difference and the SD were set based on the result of comparison between viltolarsen group and natural history control group at 25 weeks in the Phase 2 Study NS-065/NCNP-01-201 (mean difference between 2 groups: 0.0395, SD: 0.07545 and 0.07377). As the mean difference between the 2 groups at 48 weeks is expected to be larger than at 25 weeks, the mean difference was estimated to be 0.05.

An unpaired t-test for analysis was used instead of mixed effect model repeat measurement (MMRM) for the calculation method due to lack of prior information.

When approximately 90% of participants are enrolled in the study, an unblinded review will be conducted and sample size re-estimation will be considered. An additional unblinded review and re-estimation will be performed when approximately 50 participants have completed the Week 49 evaluations for the primary outcome measure. See [Section 12.8](#) for details.

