12.5.1 Efficacy Objective

The primary efficacy outcome measure (TTSTAND) will be summarized by treatment group over time using descriptive statistics.

The TTSTAND times to perform the test will also be converted to velocities. Note that a test result that is to be converted to velocity that the participant could not perform due to disease progression will have velocity set to zero only at the first visit where this occurs. After that visit, missing observations due to disease progression will be left as missing.

The TTSTAND will be compared between the viltolarsen treated participants and the placebo treated participants using MMRM analysis with treatment group, week of the visit, and the treatment-by-week interaction as factors, and age as one covariate, and baseline performance as a second covariate. The TTSTAND times to perform the test will be converted to velocities.

The treatment comparisons of most interest will be the LS means contrasts between the viltolarsen treated participants and the placebo treated participants at Week 49.

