12.5.2.2 Analysis Comparing Viltolarsen to Placebo

TTSTAND, TTRW, 6MWT, NSAA, TTCLIMB, and hand-held dynamometer results will be compared between the viltolarsen treated participants and the placebo treated participants using MMRM analysis with treatment group, week of the visit, and the treatment-by-week interaction as factors, and age as one covariate, and baseline performance as a second covariate. The TTRW and TTCLIMB times to perform the test will be converted to velocities. For a test that the participant could not perform, the velocity will be set to zero.

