12.8 Interim Analyses

Interim analysis is planned when approximately 90% of participants are enrolled in the study. An additional unblinded review and re-estimation will be performed when approximately 50 participants have completed the Week 49 evaluations for the primary outcome measure. At these 2 time points, an unblinded data review will be conducted, which will include review by the DSMB. Based on this review, the DSMB will make a recommendation to the sponsor for possible sample size re-estimation, i.e., the additional number of participants to be enrolled to increase the conditional power to an acceptable level.

Denne (Denne, 2001) described the sample size re-estimation procedure for the group sequential test by using the conditional power without inflating the type I error rate for the interim analyses. At the point at which the sample size re-estimation is being made for the interim analyses, the test statistic z_1 is observed. The conditional power is the probability of rejection H_0 on the basis that $Z_2 \geq c_2$ given $Z_1 = z_1$, which is denoted by $CP_\theta(n_2, c_2|z_1)$. The conditional power is given by:

$$CP_\theta(n_2, c_2|z_1) = 1 - \Phi \left[\frac{c_2\sqrt{n_2} - z_1\sqrt{n_1} - \frac{(n_2-n_1)}{\sqrt{2}\sigma^2}\theta}{\sqrt{n_2 - n_1}} \right]$$

where n_1 is the sample size per treatment group at the interim analyses, the true difference in mean response θ is estimated by the current sample mean difference δ , and σ^2 is estimated by the current sample within group variance s^2 . The re-estimated sample size per treatment group n_2 is obtained by solving the conditional power be at least 80% power as defined in the sample size determination. The re-estimated total sample size is given by $n^* = 2n_2$.

To preserve study integrity, a small alpha of 0.001 will be spent at the second re-estimation resulting in the overall significance level to be 0.049 at the final stage.

If the re-estimated total sample size from the interim analyses is smaller than the planned total sample size of 74, the sample size adjustment will not be needed. If the re-estimated total

sample size is larger than the planned total sample size, the sample size may be increased up to a maximum target sample size of 100.

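### The MMRM gives age and baseline one slope for all visits; if their effects change over follow-up, the Week 49 contrast loses some precision, and can be biased if age-related dropout also differs between arms

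*Combined protocol and SAP*

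**What the plan says.** Section 12.5.1 gives the primary TTSTAND velocity model as treatment group, week and "the treatment-by-week interaction as factors, and age as one covariate, and baseline performance as a second covariate". It then singles out one visit: "The treatment comparisons of most interest will be the LS means contrasts between the viltolarsen treated participants and the placebo treated participants at Week 49".

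Section 12.5.2.2 uses the same list for the secondary outcomes: "MMRM analysis with treatment group, week of the visit, and the treatment-by-week interaction as factors, and age as one covariate", with baseline performance as the other covariate. Neither section names an age-by-week or baseline-by-week term, and neither gives the covariance structure.

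Other relevant text:
- Tables 1 and 2 place post-baseline function tests at Weeks 13, 25, 37 and 49.
- Section 2.1.3 calls TTSTAND prognostic, and section 12.9 expects decline over time. Neither says how the age or baseline effect changes between visits.
- Section 12.9 plans no imputation and gives no dropout rate.
- Section 12.1 defers detail to a SAP that overrides the protocol and need only be final before database lock. The text available for review contains no SAP section.

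**The concern.** Treatment may have a different effect at each visit, but a year of age, or a unit of baseline velocity, must have the same effect at Week 13 as at Week 49. In a disease that progresses, a variable that predicts progression can be expected to relate more strongly to late values than to early ones. If so, the common slope is a compromise across visits and removes too little at Week 49, the visit that matters.

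Two things are at stake. One is precision: covariate variation that could have been removed stays in the Week 49 residual. The other is bias under dropout. The error left at Week 49 is roughly the gap between the true and the common slope, multiplied by the between-arm difference in mean covariate among boys still observed. Randomisation makes that difference zero on average at entry. Dropout can make it non-zero, but only if the arms lose different kinds of boys.

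**Working it through.** **The plan's own figure.** Section 12.2 gives "Mean difference = 0.05", "Standard deviation = 0.075", "Type I error level (two-sided) = 0.05", 80% power and 1:1 allocation. The normal approximation is n per arm = 2 × (1.960 + 0.842)² × (0.075/0.05)² = 2 × 7.85 × 2.25 = 35.3, so 36. The exact noncentral-t power is 0.797 at 36 per arm and 0.808 at 37, so 37 per arm (74 in total) is reproduced. At the 0.049 final level in section 12.8 ("resulting in the overall significance level to be 0.049 at the final stage") it is 0.805. This is an unadjusted t-test, so no covariate model enters it.

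**Models compared** (i = boy, j = visit, T = treatment, A = age, B = baseline):
- Common slope: E(Y_ij) = μ_j + τ_j T_i + β_A A_i + β_B B_i
- By-week slope: E(Y_ij) = μ_j + τ_j T_i + β_Aj A_i + β_Bj B_i

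The second adds 2 covariates × (4 − 1) visits = 6 parameters. The target is τ at Week 49.

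**Simulation inputs from the protocol:** 37 per arm, four visits, Week 49 SD 0.075, effect 0.05, ages 4 to 8.

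**Simulation inputs assumed:**
- Covariate effects rise linearly from zero, and residual SD rises with time.
- Age and baseline have equal weight and correlation −0.5, and jointly explain R² of Week 49 variance. The Week 49 slope per SD of either is then 0.075 × √(R²/3). At R² = 0.3 this is 0.0237. With uniform ages the SD is 4/√12 = 1.155 years, so the age effect is 0.0237/1.155 = 0.0205 rise/s per year at fixed baseline.
- Correlation ρ between adjacent visits is 0.5 or 0.8, with an unstructured covariance fitted.
- Dropout is none, or about 15–20%, with the odds of leaving changing by a factor e^1.5 = 4.5 per SD of age. The age pattern is the same in both arms, opposite in the two arms, or present in one arm only.

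**Results**, 1,000 runs per cell, each pair for ρ = 0.5 and 0.8. The SE ratio is common/by-week.

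| R² | SE ratio, complete data | Power, common → by-week | Bias of common slope, same dropout pattern | Bias of common slope, opposite patterns | Bias of by-week, opposite patterns |
|---|---|---|---|---|---|
| 0.1 | 0.993, 1.013 | 0.851→0.848, 0.832→0.845 | 0.0003, 0.0000 | 0.0040, 0.0053 | −0.0006, 0.0006 |
| 0.2 | 1.008, 1.038 | 0.839→0.863, 0.858→0.875 | 0.0007, −0.0002 | 0.0064, 0.0061 | 0.0000, −0.0006 |
| 0.3 | 1.039, 1.060 | 0.893→0.905, 0.887→0.909 | 0.0003, 0.0001 | 0.0085, 0.0088 | 0.0001, 0.0004 |
| 0.4 | 1.067, 1.103 | 0.924→0.957, 0.910→0.947 | 0.0007, 0.0003 | 0.0099, 0.0095 | 0.0003, 0.0002 |

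- *Noise.* The estimates have an SD of about 0.017, so a mean over 1,000 runs has a standard error of 0.017/√1000 = 0.0005. Biases up to 0.0007 under the same dropout pattern are noise.
- *Age-related dropout in one arm only* (ρ = 0.8, 1,500 runs): common-slope bias is 0.0035 at R² = 0.2 and 0.0040 at R² = 0.3, that is 0.0035/0.05 = 7% and 0.0040/0.05 = 8% of the planned effect. By-week bias is 0.0000 and 0.0001.
- *Opposite patterns:* from 0.0040/0.05 = 8% to 0.0099/0.05 = 20%. The sign depends on which arm loses the older boys. In these runs it was the treated arm, which favours the drug.
- *Constant slopes* (interactions not needed): SE ratio 0.988 and 0.983, so the extra terms cost 1/0.988 − 1 = 1.2% and 1/0.983 − 1 = 1.7%.
- *One unfavourable cell:* at R² = 0.1, ρ = 0.5 and opposite dropout, the ratio is 0.942. There the interactions remove a bias of 0.0040 at a cost of 1/0.942 − 1 = 6% in SE.

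**The case against.** The strongest reply is that most of the harm is conditional on things the documents do not show.

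- *Growing effects are assumed.* This stands. Linear growth was built into the simulation, which sizes the consequence and cannot confirm the premise.
- *A reader might infer that the contrast is biased whenever dropout depends on age.* It is not. With the same age pattern in both arms, no bias was detectable. Bias needs changing slopes and an arm difference in who leaves. Nothing in the protocol predicts such a difference, and section 2.3.3 reports no discontinuations among 16 boys in the extension study. One possible route is the section 12.5.1 rule that scores zero once for inability and leaves later visits missing. If the drug works, that missingness could differ by arm, but its frequency is unknown.
- *A reader might infer that the trial is underpowered.* It is not on this account. With complete data the common-slope model itself has simulated power of 0.83–0.92. The issue is a possible further gain of about 0 to 4 points, or up to 5 with dropout of the same pattern in both arms.
- *Baseline TTSTAND is a minimisation factor (section 5.2.1).* That limits imbalance at entry but does not control who leaves. Age is not among the factors in the visible text, part of which is blacked out.
- *Section 12.5.1 does not say whether the response is the value or the change.* This makes no difference. With baseline in the model, switching shifts its slope by exactly 1 at every visit and leaves the Week 49 contrast unchanged.
- *The SAP may already contain the terms.* This stands. The point concerns the protocol text, and it cannot be read as proof of what the final analysis will do.

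**Conclusion.** The point holds in conditional form. As written, the model imposes one age slope and one baseline slope on all four visits while the decision rests on Week 49. If those slopes change, the Week 49 standard error is larger by about 0–4% when the covariates explain up to 20% of Week 49 variance, and by about 4–10% at 30–40%. If age-related dropout also differs between arms, the bias is roughly 0.004–0.010 rise/s. The upper end needs strongly opposite dropout patterns.

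These sizes rest on the assumed linear growth, R² values, correlations and dropout, none of which the documents give. Only TTSTAND was simulated. Section 12.5.2.2 shares the model, but the effect on the secondary contrasts has no figure. With complete data, randomisation protects the Week 49 contrast from bias under either model. Severity is minor to moderate.

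**What to change.** In sections 12.5.1 and 12.5.2.2 and in the SAP, list the fixed effects as treatment, week, treatment-by-week, baseline, baseline-by-week, age and age-by-week. Fix the list before any unblinded review. Sections 12.2 and 12.8 plan two such reviews, and the SAP deadline in section 12.1 is database lock, so relying on the SAP alone could leave the primary model open after unblinded data have been seen.

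The cost is one line in each place, six more fixed-effect parameters, no new data, and about 0–2% in standard error if the slopes are in fact constant. The sample size needs no change.

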6.2 Inclusion Criteria

1. Participant's parent(s) or legal guardian(s) has (have) provided written informed consent and Health Insurance Portability and Accountability Act (HIPAA) authorization, where applicable, prior to any study-related procedures; participants will be asked to give written or verbal assent according to local requirements;
2. Participant has a confirmed diagnosis of DMD defined as:
 - a. Participant is male with clinical signs compatible with DMD; and
 - b. Participant has a confirmed DMD mutation(s) in the dystrophin gene that is amenable to skipping of exon 53 to restore the dystrophin mRNA reading frame including determination of unambiguously defined exon boundaries (using techniques such as Multiplex Ligation-dependent Probe Amplification [MLPA], comparative genomic hybridization [CGH] array or other techniques with similar capability);
3. Participant is ≥ 4 years and <8 years of age at time of first infusion in the study;
4. Participant is able to walk independently without assistive devices;
5. Participant is able to complete the TTSTAND without assistance in <10 seconds, as assessed at the Screening Visit and the Pre-infusion Visit. (Note: The TTSTAND performed independently from the NSAA should be used to determine eligibility.);
6. Participant and parent(s)/guardian(s) are willing and able to comply with scheduled visits, study drug administration plan, and study procedures;
7. Participant must be on a stable dose of GC for at least 3 months prior to first dose of study drug and is expected to remain on the stable dose of GC treatment for the duration of the study.

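### The primary model names one undefined baseline covariate although TTSTAND is measured at two pre-dose visits; using both is a cheap and probably modest gain in precision

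*Combined protocol and SAP*

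**What the plan says.** - **Primary model (Section 12.5.1).** An MMRM on TTSTAND velocity with treatment, week and their interaction, age, and "baseline performance as a second covariate". The contrast of interest is at Week 49. Section 12.5.2.2 uses the same covariates for the other function and strength tests. Neither section says which visit or rule supplies the baseline.
- **Two pre-dose measurements.** Table 1 and Sections 10.1.1 and 10.1.2 schedule TTSTAND at Screening and again at Pre-Infusion. Inclusion criterion 5 (Section 6.2) requires a time under 10 seconds "as assessed at the Screening Visit and the Pre-infusion Visit", so every eligible boy should have both values. Section 10.2.1 lists no function test on Day 1.
- **Two forms of the test (Section 9.15.1.1).** The rise is timed as an independent test and again within the NSAA. The independent test is singled out only for eligibility.
- **Allocation (Section 5.2.1).** Baseline TTSTAND is also a minimization factor. No visit is named in the visible text, and part of that section is blacked out.
- **Other uses of baseline.** A visit is attached only for safety data: screening for ECG abnormalities (Section 11.12) and Day 1 for laboratory, vital-sign and ECG changes (Section 12.6.1). Neither can settle TTSTAND.
- **SAP (Section 12.1).** Further detail is left to a SAP that overrides the protocol where they differ. The text supplied contains no separate SAP section.

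**The concern.** A single timed rise in a boy of 4 to 7 years carries day-to-day error, and error in a covariate weakens the adjustment it provides. With 37 boys per arm, the width of the confidence interval for the Week 49 difference depends on how much outcome variance the baseline explains. A second pre-dose value from the same test, at most four weeks from the first, is already in the schedule. If the model uses only one value, that information is lost for no saving.

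A smaller point concerns pre-specification. Two visits and two forms of the test give up to four candidate pre-dose values per boy, before any repeats allowed under Sections 6.3 and 9.3.1. The choice among them should be closed before anyone sees data by arm.

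**Working it through.** **1. The plan's own sample size.** Inputs from Section 12.2: "Mean difference = 0.05", "Standard deviation = 0.075" (set from Phase 2, "SD: 0.07545 and 0.07377"), "Type I error level (two-sided) = 0.05", "Power level = 0.8", 1:1 allocation, unpaired t-test.

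The noncentrality is 0.05 / (0.075 × √(2/n)). At n = 37 per arm this is 0.05 / 0.01744 = 2.87, and the noncentral t distribution on 72 df gives power 0.808. At n = 36 power is 0.797. So 37 per arm, 74 in total, is reproduced. At the final level in Section 12.8 ("resulting in the overall significance level to be 0.049 at the final stage") power is 0.805. No baseline correlation enters, so the choice of baseline cannot change the 74.

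**2. Gain if the two visits predict equally well.** ANCOVA approximation to the Week 49 contrast. Let ρ be the correlation of one pre-dose value with Week 49, and r the correlation between Screening and Pre-Infusion. Both are assumptions, because the documents give neither, and they are best read as correlations given age, which is already in the model.

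- One baseline: residual variance ∝ 1 − ρ²
- Both baselines: residual variance ∝ 1 − 2ρ²/(1 + r)
- Equivalent extra boys: 74/(variance ratio) − 74

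| ρ | r | Variance ratio | Fall | Extra boys |
|---|---|---|---|---|
| 0.6 | 0.95 | 0.631/0.640 = 0.986 | 1.4% | 1.1 |
| 0.7 | 0.90 | 0.484/0.510 = 0.949 | 5.1% | 3.9 |
| 0.7 | 0.85 | 0.470/0.510 = 0.922 | 7.8% | 6.3 |
| 0.8 | 0.85 | 0.308/0.360 = 0.856 | 14.4% | 12.5 |

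In the middle case the standard error is multiplied by √0.949 = 0.974.

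**3. If Screening predicts less well.** Write ρS and ρP for the two correlations with Week 49. The mean of the two values has correlation (ρS + ρP)/√(2(1 + r)) with Week 49. It does worse than Pre-Infusion alone when ρS/ρP is below √(2(1 + r)) − 1, which is 0.92, 0.95 and 0.97 for r = 0.85, 0.90 and 0.95.

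Example with ρP = 0.70, ρS = 0.65, r = 0.90:

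- Mean: 1.35/√3.8 = 0.6925, and (1 − 0.4796)/0.51 = 1.02, a 2% loss.
- Two separate covariates: R² = (0.49 + 0.4225 − 2 × 0.70 × 0.65 × 0.90)/(1 − 0.81) = 0.4921, and (1 − 0.4921)/0.51 = 0.996, no asymptotic loss.

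**4. Finite-sample cost of the extra covariate.** With normal covariates and simple randomization, the variance of the contrast is inflated by (N − 3)/(N − p − 3) for p covariates. Going from two covariates (age, one baseline) to three at N = 74 multiplies it by 69/68 = 1.015. For two covariates the middle case becomes 0.949 × 1.015 = 0.963. The low end becomes 0.986 × 1.015 = 1.00, and the example in step 3 becomes 0.996 × 1.015 = 1.01. Minimization on baseline TTSTAND should make this cost smaller. The mean does not incur it.

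**5. Power at the planned difference (ρ = 0.7, r = 0.90, before the cost in step 4).**

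- If 0.075 is the SD of change and variances are equal at the two times, the outcome variance is 0.075²/(2 × 0.3) = 0.009375. The residual SD falls from 0.0691 to 0.0674, and power rises from 0.866 to 0.883.
- If 0.075 is the SD of the Week 49 value, the residual SD falls from 0.0536 to 0.0522, and power rises from 0.977 to 0.982.

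**The case against.** The best case for leaving the plan alone has four parts.

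- **One pre-dose baseline is valid.** It biases nothing and leaves the type I error intact. This stands. The point is about efficiency and pre-specification only.
- **The visits may not predict equally.** Screening is earlier, is the first exposure to the test in this study, and may be repeated at the investigator's discretion or under rescreening. This stands against taking the mean automatically. Against it, the visits are at most four weeks apart with about 48 weeks to the endpoint, and Section 9.15.1 asks for the same evaluator where possible. Near-equal prediction is plausible but not shown.
- **Power is less tight than 0.808 suggests.** The t-test sizing takes no credit for covariate adjustment. This also stands: at ρ = 0.7 a single baseline already gives 0.866 or 0.977, and the second value adds 1.7 or 0.5 percentage points.
- **The definition may exist elsewhere.** Section 12.1 points to a SAP, and Section 5.2.1 is partly blacked out. A reader might infer that the sponsor has left the baseline open. The documents show only that the supplied text does not define it.

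None of this is a reason to discard a measurement already taken, or to leave the covariate undefined in the section that specifies the primary analysis.

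**Conclusion.** The point holds as an optional, inexpensive improvement. There are two pre-dose TTSTAND visits and one baseline covariate, and the supplied text has no rule linking them. For equally predictive visits, with ρ from 0.6 to 0.8 and r from 0.85 to 0.95, using both lowers residual variance by about 1.4% to 14%. The middle case is 5%, about 4 boys of 74, or about 3 if both enter as covariates and the extra parameter is charged in full (74/0.963 − 74 = 2.8).

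Two stronger readings are tempting and are not supported. The first is that averaging certainly sharpens the Week 49 contrast at no cost. That requires near-equal prediction, which the documents do not establish, and the mean loses about 2% when the correlations are 0.65 and 0.70 at r = 0.90. The second is that the trial is mis-sized: 74 reproduces exactly and does not depend on the baseline. All the gains rest on assumed correlations and on an ANCOVA approximation to the MMRM.

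**What to change.** In Section 12.5.1, or in the SAP, before the first unblinded review at about 90% enrolment:

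- State that the model uses the TTSTAND velocities from the independent test, not the NSAA rise, at both Screening and Pre-Infusion.
- Enter them as two separate covariates, or as the mean of the two velocities if the sponsor is willing to take the visits as about equally predictive. Two covariates protect against unequal prediction for about one degree of freedom; the mean saves that degree of freedom but carries the risk in step 3.
- If one value is missing, use the available one. State which value counts when a test or a screening is repeated.
- State how this baseline relates to the TTSTAND value used in minimization.
- Apply the same rule to the other tests on their own scales: velocity for TTRW and TTCLIMB, metres for 6MWT, total score for NSAA, force for dynamometry.

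The cost is a few sentences, with no new visit, test or data. If the mean is used, change-from-baseline summaries should use it too. A sponsor who prefers Pre-Infusion alone still needs to write that down by the same date.
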